Appendix J: Trust and Communication Survey (Prevention RN – PLHIV participant)

Enter the participant ID

Please indicate the study visit:

- Baseline visit (0)
- 4 month visit (1)
- 8 month visit (2)
- 12 month visit (3)

Please think of your relationship with the patient you listed above. For the validity of this study, please answer honestly. Recall your answers are confidential and will never be shared with any provider, patient nor anyone else outside our research team. Some of the questions may sound repetitive, but please read fully before answering each question.

Please rate the following statements based on your recent interaction with this patient.

	Strongly Disagree (1)	Disagree (2)	Neither Agree nor Disagree (3)	Agree (4)	Strongly Agree (5)
Overall, I trust this patient.					
Overall, I am satisfied with my communication with this patient					
Overall, I have a good relationship with this patient.					

Thank you! To rate another participant, please open a new survey.

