Familial Hypercholesterolemia	
DO NOT include the following:	DO NOT include the following:
Low HDL	Pulmonary hypertension
	Intracranial hypertension
	Venous hypertension
	Pre-eclampsia or Maternal Hypertension
	Portal hypertension
	Ocular hypertension

Randomization: Prior to study start, [name] will develop a 1:1 blocked randomization scheme, stratified by site. This randomization scheme will be carried out using the randomization module in RedCap. Participants will be randomized by RedCap at the time of their baseline visit to avoid randomizing participants who have not yet completed consent.

Education control group: Participants assigned to the education group will receive usual care enhanced with general prevention education delivered by the prevention nurse. This active comparator is appropriate because participants have multiple risk factors for ASCVD, and advisory committees for prior studies have recommended this for similar study populations. The prevention educational modules will be delivered at 4 in-person visits (enrollment, 4, 8, and 12 months), and will consist of evidence-based material on diet, exercise, smoking, sexually transmitted infections, and cancer prevention. As recommended by the design teams, control participants will have access to a wide range of educational materials about healthy living, but will not receive additional counseling from the prevention nurse outside of the 4 in-person visits.

All participants in both intervention and education control arms will complete the following study assessments: 1) in-office BP obtained by a trained research assistant blinded to study group using a standardized protocol¹² (0, 4, 8, 12 months); 2) lipid profile (0, 4, 8, 12 months); 3) perceived ASCVD risk survey⁵⁶ (0, 12 months); 4) provider trust and communication survey (0, 12 months). Study visits will be calculated from the date of the baseline enrollment visit in months. Per protocol, study visits must be completed +/- 14 days from the calculated visit date.

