Visits done between 14 and 28 days after the calculated visit date will be considered a protocol deviation. Visits outside of the +28 day window will not be scheduled and that visit will be considered missing for that patient. The fasting lipid panel blood draw will be done at the time of study visit or within a +/- 10 day window. To limit potential bias, participants, their healthcare providers, and the prevention nurse delivering the education modules will be blinded to the in-office BP outcome measure unless a safety threshold is exceeded (systolic BP <90 or >180mmHg). BP may be re-checked separately as part of routine care.

Control participants will be encouraged to maintain participation in the study in order to minimize differential loss-to-follow-up between intervention and control group that would jeopardize the validity of study findings. As recommended by the design teams, we will conduct semi-annual participant engagement parties (in January and July) that will consist of a meal, healthy lifestyle education and games. We will report enrollment and other study related news to participants. All participants—both intervention and control—will be invited to these events. As an additional incentive, control participants will receive a BP monitor and instructions about its use after completion of the final 12-month trial visit.

EXTRA-CVD intervention: Participants randomized to the intervention will meet with the site prevention nurse on the day of enrollment. With nurse assistance, the participant will complete an initial ASCVD risk assessment using the ACC/AHA risk calculator and a risk visualization tool available at <https://statindecisionaid.mayoclinic.org/>. This exercise will help establish rapport between the participant and the nurse, and will help identify potential targets for intervention. The nurse will conduct a baseline medication assessment, including participant's knowledge of the purpose and side effects of each BP or cholesterol medication and current or potential adherence strategies.

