Under PI-[name]'s direction, all responses will be analyzed using standard analytic techniques for qualitative data: identification of themes/domains; coding or classification of participants' responses by these themes performed independently by two team members (who have graduate-level training in qualitative coding); resolution of any coding discrepancies will be done by a third team member.⁷⁸ To ensure consistency, a codebook and dictionary will be developed to create universal definitions for each code. The codebook will contain all codes, their definition, and exemplar quotes.

PLHIV-Provider Trust & Communication Ties

The success of the EXTRA-CVD intervention to improve blood pressure and cholesterol may depend on the nature of the personal relationship between PLHIV participants and his/her providers, including the prevention nurse. Therefore, we have designed our own tool, based on validated surveys used in social network analyses, to assess the strength of trust and communication ties between PLHIV participants and providers as well as ties between the prevention nurse and health care providers/staff. There will be three sources of data for this part of the process evaluation:

1. Survey completed by the PLHIV participant about each of his/her healthcare team members. This survey will be completed at each in-person visit. (**Appendix I**)
2. Survey completed by the prevention nurse about each PLHIV participant after each in-person visit. (**Appendix J**)
3. Survey completed by the prevention nurse about providers encountered during the course of the trial (completed every 3 months only for those providers with whom the prevention nurse interacted during that quarter). (**Appendix K**)

Confidentiality of trust and communication survey responses is especially important. To that end, we have designed these surveys in a way that it is not possible to link responses to individual persons as follows:

1. The surveys will not be conducted in redcap. Instead, a Case Western Qualtrics platform will be used. The survey links for all sites will be maintained by one study coordinator at

- the UH/Case Western site. No PHI will be entered into this platform.

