2. The prevention nurse at each site will keep a key of unique identifiers for each provider within a patient's care team network. The prevention nurse will keep this in a password protected file on his/her own personal network drive (to ensure that it is backed-up). The prevention nurse will be the only one with access to this file.
 3. The nurse will prepare the participant who is taking the survey by helping the participant enter the unique identifier for his/her HIV provider, HIV-nurse, primary care provider, or non-HIV specialist. The participant will then complete the same set of survey questions for each of his/her providers.
 4. On a quarterly basis, or when not fewer than 10 complete records have accumulated, the UH/Case Western study coordinator will compile the survey data and link it to exported RedCap data using a statistics software program (STATA 13.0).
 5. This completely deidentified dataset will then be sent to two consultants with expertise in social network analysis ([name], UT Dallas and [name], U North Texas) who will conduct the analyses.
 6. Results will be reported anonymously by site (site A, B, and C), prevention RN (RN1, RN2, RN3) and provider (HIV provider 1, PCP 1, etc...).

Analyses: The primary analysis will be to test the intervention effect on PLHIV-Provider trust and communication ties, using a similar repeated measures analysis as described below for the primary BP and secondary cholesterol outcomes. As an exploratory analysis, we will assess whether the effect of the EXTRA-CVD intervention on the primary BP and secondary non-HDL outcomes are mediated by changes in trust and communication ties. Additional exploratory analyses will be conducted to assess the effect on the balance of trust/communication ties between HIV vs. non-HIV providers and to assess the longitudinal change in prevention RN-provider trust and communication over the course of the intervention.

Aim 4 Procedures:

Intervention Adaptation

The intervention will be adapted with the assistance of stakeholder design teams that have already been convened in Cleveland and Durham as part of our original intervention adaptation sub-aim 1.1. We now propose an additional round of design iteration to make virtual adaptations for this aim. Members of both design teams will be invited to attend combined virtual design sessions hosted in Zoom.

Adaptation Description

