The primary outcome will be systolic BP at 12 months and secondary outcome will be non-HDL cholesterol at 12 months, both measured at 4 time-points (0, 4, 8, and 12 months). All BPs used for outcomes will be obtained by a blinded research assistant and cholesterol levels will be measured by lab personnel who are also blinded to treatment group. Because the outcomes are continuous, linear mixed-effects models⁸⁹ (LMM) will be used to examine the differences over time between the study arms. LMM will allow us to implicitly account for the correlation between a patient's repeated measurements over time. The general mean structure of the LMM we will use to examine the hypotheses is, $Y_{ij} = \beta_0 + \beta_1 * I(month = 4) + \beta_2 * I(month = 8) + \beta_3 * I(month = 12) + \beta_5 * arm * I(month = 4) + \beta_6 * arm * I(month = 8) + \beta_7 * arm * I(month12)$, where Y_{ij} represents the outcome of interest (i.e., SBP or non-HDL) for patient i at time j . In this model, we fit a common intercept and arm is the intervention group indicator. Similarly, time is classified, where for example, $I(month = 12)$ is a dummy variable equal to 1 for the 12 month time point. Random intercepts will be included for

each individual to account for correlation among repeated measurements over time. The primary analytic model will adjust for clinic site. The mixed effects model parameters will be estimated and tested using SAS PROC MIXED (SAS Institute, Cary, NC), and the hypothesis of between-arm differences over time will be tested using estimate statements within PROC MIXED. In particular, β_7 , the estimated difference in outcome between arms at 12 months, will be the primary effectiveness outcome assessed.

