Appendix I: Trust and Communication Survey (PLHIV participant – Provider)

As a participant in the EXTRA-CVD study, we are asking you to complete a survey about your relationship with your healthcare providers. You will need at least 15 minutes of uninterrupted time to take this survey. If you have any questions, please see your EXTRA-CVD nurse or study coordinator. Please understand that your answers will be confidential. More specifically, your name and the names of your providers will never be recorded with your data. The unique ID numbers will be kept separately by study staff at your site who do not have access to the survey results. Please respond below in order to proceed:

- Yes I understand my rights as a participant in this study. I consent to proceed.
- No I do not consent and will not participate in this study and survey

Please enter here your unique participant ID. EXTRA-CVD study staff will ensure that you enter your correct ID. PLEASE DO NOT LIST YOUR NAME.

Please select which visit you completed today as part of this study. EXTRA-CVD study staff will ensure that you select the correct answer.

- Baseline visit
- 4 months visit
- 8 months visit
- 12 months visit

As a participant of this study, in the following sections, you will be asked some questions regarding your relationships with providers that may help treat your HIV or your blood pressure and cholesterol. At a minimum, this will include: your HIV provider and your EXTRA-CVD nurse.

Additionally, you may be asked some questions about the rest of your health care providers (for example, your Primary care physician, your HIV clinic nurse or you Non-HIV specialists).

Protocol

We hope to collect quality data for our research. But If you feel uncomfortable to answer any of the questions or feel that a question is not applicable to you, feel free to skip it.

Do you have a HIV clinic nurse?

Yes

No

Do you have a Primary care physician?

Yes

No

Please indicate which of the following medical professionals primarily treats your blood pressure (if multiple physicians care equally for your blood pressure, please select all that apply):

My HIV provider

My HIV clinic nurse

My Primary care physician

My Non-HIV specialist, please specify the specialist type (i.e.; cardiologist, nephrologist, endocrinologist): _____

No one manages my blood pressure

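### The prevention nurse's month-0 trust rating follows randomisation and the first session, so reusing the common-intercept model would take part of any first-session difference out of the 12-month nurse-tie effect

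*Combined protocol and SAP*

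**What the plan says.** **Timing.** Appendix J lists the baseline visit, coded 0, as the first of four rating occasions, with the instruction "Please rate the following statements based on your recent interaction with this patient". The protocol's section on PLHIV-Provider Trust & Communication Ties (Aim 3 Procedures) describes this source as "Survey completed by the prevention nurse about each PLHIV participant after each in-person visit". Under Aim 2 Procedures, the Randomization paragraph says "Participants will be randomized by RedCap at the time of their baseline visit to avoid randomizing participants who have not yet completed consent", and the EXTRA-CVD intervention paragraph says "Participants randomized to the intervention will meet with the site prevention nurse on the day of enrollment". That paragraph describes a joint risk-assessment exercise meant to build rapport. The Education control group paragraph has the same nurse give controls their first module at enrolment.

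**Which ties are rated.** The introduction to the ties section counts the prevention nurse among the participant's providers. Appendix I says of the participant's own survey: "At a minimum, this will include: your HIV provider and your EXTRA-CVD nurse".

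**Model.** The primary analysis of the ties is a test of the intervention effect "using a similar repeated measures analysis as described below for the primary BP and secondary cholesterol outcomes". For that blood-pressure and cholesterol model, Statistical Considerations states "In this model, we fit a common intercept and arm is the intervention group indicator". It has month dummies, arm-by-month terms for months 4, 8 and 12, a random intercept per person, and no arm term at month 0. The SAP repeats this model but covers Aim 2 only. Nothing in the documents provides a pre-randomisation rating of the nurse tie, or a different treatment of month 0 for it.

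**The concern.** A common intercept fixes the arm difference at month 0 to zero. Randomisation justifies that for a value recorded before allocation. It does not justify it for a rating recorded after allocation and after a session that, in one arm, is meant to strengthen the relationship being rated. If the two first sessions move the rating differently, the model treats the resulting gap as chance imbalance and adjusts the 12-month contrast for it.

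What is at stake is the 12-month effect on the nurse tie, within the analysis that the protocol calls primary for this part of Aim 3. The exploratory mediation of the blood-pressure and non-HDL effects is also exposed. A mediator defined as change in the tie since month 0 would leave out whatever the first session achieved.

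**Working it through.** **Inputs.** The model is the one in Statistical Considerations. No SD, correlation or expected effect is given for the trust scores. As a range for r, I borrow the two within-person correlations in the Power section: 0.4 (SBP) and 0.7 (non-HDL). The values D12 = 0.5 SD and d0 = 0 to 0.3 SD are assumptions for illustration.

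**Check of the model code.** The plan has no power figure for ties to reproduce. The same generalised least squares set-up, with 300 participants and 5/10/15% dropout, gives 87% power for 6 mmHg and 98.5% for 15 mg/dL. These agree with the plan's >80% and >90%.

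**Formula.** A random intercept implies equal variances and one correlation r between any two visits. With the month-0 means forced equal, the fitted 12-month contrast is the observed arm difference at month 12 minus r times the observed arm difference at month 0. Its expectation is

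E[β7] = D12 − r·d0, so the fraction lost is r·d0 / D12.

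Solving the normal equations gave the same values with complete data and with 5/10/15% monotone dropout.

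**Results for D12 = 0.5 SD.**

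| d0 (SD) | E[β7], r = 0.4 | loss | E[β7], r = 0.7 | loss |
|---|---|---|---|---|
| 0 | 0.50 | 0% | 0.50 | 0% |
| 0.1 | 0.46 | 8% | 0.43 | 14% |
| 0.2 | 0.42 | 16% | 0.36 | 28% |
| 0.3 | 0.38 | 24% | 0.29 | 42% |

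Example: 0.5 − 0.7 × 0.3 = 0.29, and 0.21 / 0.5 = 42%. If d0 were −0.1 SD the estimate would be too large: 0.5 + 0.4 × 0.1 = 0.54, or 0.5 + 0.7 × 0.1 = 0.57.

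**Simulation.** REML fits with n = 300, r = 0.4, d0 = 0.2 and D12 = 0.5 should average 0.42. One set of 200 runs gave 0.404 (Monte Carlo SE 0.007) and one of 800 gave 0.425 (SE 0.004). Pooled: (200 × 0.404 + 800 × 0.425) / 1000 = 0.421.

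**The remedy in the same model.** With an arm-by-month-0 term and no arm main effect, each visit has its own arm difference, and the 12-month coefficient has expectation D12. In 60 simulated trials per setting, with a true difference of 0.30 SD at month 0 and at month 12, the common intercept gave 0.173 (r = 0.4) and 0.078 (r = 0.7). The model with the added term gave 0.288 and 0.299.

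**A coding trap.** If an arm main effect is added and only the arm-by-month-12 interaction is read, the result is D12 − d0. That subtracts all of d0: 0.5 − 0.2 = 0.30.

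**Precision cost.** With complete data the constraint multiplies the variance of the 12-month contrast by 1 − r². Dropping it raises the SE by 1/√(1 − 0.16) = 1.09 or 1/√(1 − 0.49) = 1.40.

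**The case against.** Several points on the other side are fair.

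- **Timing is documented for one survey only.** The rating after the visit is stated for the nurse's Appendix J form. Appendix I asks which visit was completed that day, which hints at the end of the visit. No text orders it against randomisation or the first session. This stands, so Appendix I is only a possible case.
- **A prior tie is possible.** A reader might infer that nurse and participant cannot know each other before allocation, so that no pre-randomisation rating could exist. The documents do not say so. The safety text on blood pressure describes the research nurses as integrated in their clinics, although the Appendix L checklist has the nurse introduce herself or himself. The point does not need this inference: with or without earlier acquaintance, the Appendix J rating comes after the session.
- **The model is only similar.** The protocol does not write out a tie model. Carrying over the common intercept is the natural reading, not a stated choice. It is also not stated whether Appendix J enters the primary tie analysis. The item stem in Appendix I and the survey instructions name HIV and other providers without the prevention nurse.
- **The size is unknown.** Controls meet the same nurse on the same day, so d0 is a difference between two sessions. It may be zero or negative.
- **The outcome is a process measure.** Aim 3 is descriptive, the mediation analysis is exploratory, and a positive d0 makes the estimate conservative.

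These limit the reach and size of the point. They do not supply a reason to assume d0 = 0 for a rating taken after a session meant to build rapport.

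**Conclusion.** The point holds in conditional form. The nurse's month-0 rating in Appendix J is a post-randomisation measurement. If the tie analysis keeps the common intercept, the 12-month nurse-tie effect is estimated as D12 − r·d0. Under the illustrative values above the loss is 0 to 42%. It is nil if the first sessions do not differ in their effect on the rating, and it reverses if d0 is negative. The correlations are borrowed from SBP and non-HDL, and nothing shows that they apply to trust ratings.

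A reader might infer a loss of 40 to 70% of the effect. That is r itself, and it requires the whole 12-month difference to be present after a single session (d0 = D12), which no document supports. A reader might also infer that the trial's main results are at risk. They are not: SBP and non-HDL are outside this point, which concerns the Aim 3 tie analysis and its exploratory use in mediation. It is a modest point with an inexpensive correction.

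**What to change.** In the Analyses paragraph of the trust and communication section:

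1. State whether the two nurse ties (nurse rating participant, participant rating nurse) enter the tie analysis.
2. For any nurse tie rated after randomisation, treat month 0 as an outcome. Add arm × I(month = 0) to the existing arm-by-month terms, include no arm main effect, and report the 12-month coefficient as the total arm difference. The month-0 coefficient then estimates the first-session difference itself.
3. Do not define the mediator as change from that month-0 rating.
4. Keep the common intercept only for ties rated before randomisation, and record whether the Appendix I ratings were.
5. Reconcile the survey schedule. The assessment list in Aim 2 Procedures gives months 0 and 12. The Aim 3 text gives every in-person visit, and Appendices I and J list four visits. Starting the response at the first follow-up rating is a workable alternative only once this is settled, because under the two-visit schedule it leaves a single time point.

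The cost is a few sentences and no new data. The SE for the nurse ties rises by about 9% (r = 0.4) to 40% (r = 0.7). The precision given up rests on assuming equal arms at a visit where that assumption is not secured by randomisation.

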Appendix K: Trust and Communication Survey (Prevention RN – Provider)

Please input only the unique identifier of the provider (do not enter any names!) that you will be rating in the next set of questions. Please verify this ID is correct before continuing.

Please rate the following statements based on your recent interactions (since the last survey) with this provider. Your responses to these questions may or may not change over time as you continue to interact with this provider over the course of the EXTRA-CVD intervention.

	Strongly Disagree	Disagree	Neither Agree nor Disagree	Agree	Strongly Agree
Overall, I trust this provider.					
Overall, I am satisfied with the communication with this provider.					
Overall, I have a good relationship with this provider.					

Do you have another provider to rate?

Yes

No

Appendix L: Study staff and prevention nurse observation checklist to ensure intervention fidelity.

Study Staff Observation Checklist:

Date:

Observer:

Location:

Setup:

Checked that Blood Pressure (BP) machines are functional and available

Knew the directions to the blood lab and the working hours

Explain and correctly perform blood pressure procedures (study staff NOT prevention nurse):

Participant was sitting with feet on the floor

Participant's arm was at heart level

Participant removed extra clothing (coat/jacket must be removed; long sleeve shirts may remain on)

Participant was encouraged to relax

Participant was not talking during measurement

- If participant was talking, measurement was repeated

BP cuff was well placed above the elbow and admitting two fingers

Correct size of BP cuff was used

Two BPs were obtained, 1 minute apart

Blood pressure was checked in both arms

Informed consent:

Explained purpose of research study

Explained description of procedure

Explained confidentiality of study data

Explained potential benefits

Explained potential risks

Explained voluntary participation and rights to discontinuation

Checked understanding with open questions. “Could you tell me what’s going to happen if you enroll in the study?”)

Checked understanding with closed questions (e.g. “Will you get free medications from the staff of this research study?” or “what will happen to your medical care after the study?”)

Corrected misconceptions (eg: Patient thinks they will get free medications or patient thinks they don’t have to follow up with their doctor after this study is done”) and recheck understanding.

Filled the informed consent checklist

Requested signature or participant thumbprint

Asked if participant has any questions

Data collection:

Explained how to use REDCap to the participant

Appropriately gathered medical history data from chart review

Appropriately answered questions about how to respond to individual survey questions

Prevention nurse procedures checklist:

Date:

Observer:

Location:

Establishing Rapport:

- Introduced herself/ himself to the patient
- Made eye contact with the patient
- Listened to the patient
- Was able to engage patient in the conversation

Counselling: Baseline

- Asked patient for the purpose and side effects of his/her current medications
- If a new medication is added, PN discussed purpose and side effects of the medication, and any required follow up
- Discussed strategies for medication adherence
- Discussed non pharmacological targets for blood pressure control
- Asked patient for their preferred primary provider
- Discussed methods of home BP monitoring
- Set expectations with the patient about follow up phone calls and visits
- Informed primary and non primary providers of plan at the end of visit

Counselling: Follow up

- Asked patient for home BP values over the last 2 weeks
- Checked patient's understanding of the method of home BP measurement.
- Reviewed patient's medication list and adherence
- If patient is non- adherent, prevention nurse discussed reasons for non-adherence (Eg. side effects, cost, timing etc.)

Protocol

If a new medication is added, prevention nurse discussed purpose and side effects of the medication, and any required follow up

Referred patient to the blood lab for a lipid panel

Set expectations for follow up phone call and visits

Informed primary provider and non primary provider of updated plan

Appendix M: Behavior Change Counseling Index (BECCI) to Measure Practitioner’s Motivational Interviewing Skills

Date: Staff and Role: Observer:		Strengths: Area for Growth: Scoring: 0 = Not at all, 1 = Minimally, 2 = To some extent, 3 = A good deal, 4 = A great extent, or N/A		
Item	Description	Score	N/A	Comments
1. Invites the person to talk about behavior change*	Explicitly asks permission to talk about behavior change. Conveys person is not obligated to make a decision.			•
2. Demonstrates sensitivity to talking about other issues	Person is given choice in what to talk about; use of agenda setting.			•
3. Encourages person to talk about current behavior/status quo	Encourages person to talk freely about the benefits and limitations of current behavior. Uses open-ended questions to elicit person’s perspective and reflections to convey understanding.			•
4. Encourages person to talk about change	Encourages person to talk freely about the benefits and limitations of making a behavior change. Uses of open-ended questions to elicit person’s perspective and reflections to convey understanding.			•
5. Asks questions to elicit how person thinks and feels about topic	Uses open-ended questions to elicit person’s thoughts and feelings related to a behavior change			[Closed Questions – CQ] • [Open Questions – OQ] •

Protocol

6. Uses reflective listening when the person talks about the topic	Uses reflections to convey understanding, clarify understanding of what the person has said and encourage further patient elaboration.			•
7. Uses summaries to bring together what the person says about the topic	Uses periodic summaries (collecting, linking, transitional) to check understanding, assists person to hear what they have said and/or transition to a new task (i.e., change planning)			•
8. Acknowledge challenges about behavior change that the person faces	Uses reflections to convey understanding that change is difficult and affirm the person's strengths			•
9. When providing information it is sensitive to person's concerns and understanding*	Attempts to understand what the person knows, wants to know and elicits their understanding of information provided and/or reaction to information provided. N/A if no information requested or shared			•
10. Staff and person exchange ideas about how the person could change current behavior*	Uses open-ended questions to encourage person to brainstorm strategies that support behavior change; person offers most of the ideas; permission to disregard and multiple ideas are offered when staff makes suggestions. N/A if person is not ready to plan for change			•
BECCI Overall (Average) Score				
11. Staff speaks for approximately	
 • More than half the time • About half the time • Less than half the time 			•

MI Skill Development Plan

Name:

Date:

Strengths Demonstrated in Session		
Skill Development		
MI Skill Targeted for Improvement	What specifically will be developed or improved?	How will the goal be reached?

Appendix O. Functional Assessment of Currently Employed Technology Scale (FACETS), Copyright 2018 [name]

A.	Home Domain						
1.	I send email...	 Never	 A few times a year	 A few times a month	 Once a week	 A few times a week	 Daily
2.	I find, open & close files in my computer...	 Never	 A few times a year	 A few times a month	 Once a week	 A few times a week	 Daily
Home Domain Subtotal							
B.	Social Domain						
3.	I send text messages using a smart phone...	 Never	 A few times a year	 A few times a month	 Once a week	 A few times a week	 Daily
4.	I post on social media (e.g., facebook, twitter)...	 Never	 A few times a year	 A few times a month	 Once a week	 A few times a week	 Daily
Social Domain Subtotal							
C.	E-Commerce Domain						
5.	I manage my banking and credit card accounts online...	 Never	 Tried, but it didn't work	 Got help but didn't work	 Only with help	 Can but prefer not to	 Prefer to
6.	I pay bills and make purchases via the internet...	 Never	 Tried, but it didn't work	 Got help but didn't work	 Only with help	 Can but prefer not to	 Prefer to
E-Commerce Domain Subtotal							
D.	Health Care Domain						
7.	I communicate with my doctor or clinic online...	 Never	 Tried, but it didn't work	 Got help but didn't work	 Only with help	 Can but prefer not to	 Prefer to
8.	I communicate with my health insurance company online...	 Never	 Tried, but it didn't work	 Got help but didn't work	 Only with help	 Can but prefer not to	 Prefer to
Health Care Domain Subtotal							
E.	Technical Domain						
9.	I have installed components (monitors, speakers, mice)...	 Never	 Tried, but it didn't work	 Got help but didn't work	 Only with help	 Myself, with difficulty	 Myself easily
10.	I have reset a modem or router in my home...	 Never	 Tried, but it didn't work	 Got help but didn't work	 Only with help	 Myself, with difficulty	 Myself easily
Technical Domain Subtotal							
Total FACETS Score							

